6.4.2.2 Placebo

Daily dose of placebo matching to VIT-2763, to be taken orally from Day 1 to Day 84 as per randomisation scheme and schedule. Capsules are to be taken in the morning in conjunction with water approximately 1 hour after meals between approximately 08:00 to 10:00 a.m. At study visits, subjects are asked to stay in the hospital until up to 4 hours at selected visits for PK sampling. At 2-3 hours post administration a 12-lead ECG will be conducted. To maintain the BID dosing schedule, i.e., after having received a dose in the morning at the hospital, the subjects will be advised to take the study medication in the evening approximately 1 hour after meals and with water at approximately the same clock time each day between 8:00 p.m. and 10:00 p.m. in the evening.

The placebo will match the VIT-2763 dosage strength (60 mg) used.

6.5 Package and Labelling

VIT-2763 60 mg and matching placebo capsules in HDPE bottles will be supplied to the investigational site as double-blind medication.

Medication labels will comply with local requirements.

6.6 Study Treatment Allocation

Each eligible subject will be randomly assigned to 1 of the 3 treatment arms (VIT-2763 QD or BID, or placebo) through a secure and validated centralised IWRS as described in Section 6.4.1. The IWRS will specify the unique medication number(s) for the study drug to be dispensed to the subjects.

6.7 Site Supply, Storage, Accountability

6.7.1 Site Supply

Once the site has been approved to receive study drug, the site will be supplied with an initial stock of VIT-2763 (dosage strength 60 mg and placebo). The need for IMP resupply will be assessed on a regular basis taking into account the number of subjects enrolled or randomised, and the number of subjects in screening at the site. If a subject is not able to visit the site for IMP resupply due to COVID-19 pandemic, a direct shipment of the study drug to the patient home/place of stay can be implemented, if allowed by the local regulations. The shipment will be performed by a logistics provider in a traceable and temperature-controlled manner and will be documented adequately. Written information on the dose regimen will be provided to the patient along with contact information to site for any questions patient may have. The subject will return any unused IMP and empty IMP packages with a logistics provider or during the next on-site visit as instructed by the Investigator.

6.7.2 Storage

Upon receipt, all IMPs should be stored according to the instructions specified on the drug labels and accessible to authorised personnel only. The site should have a calibrated thermometer that records minimum and maximum temperatures daily, or the temperature should be monitored continuously using a continuous temperature monitoring system. Maintenance of a temperature log is mandatory. The log should be updated by site personnel daily. This log must be available for review by the Monitor/Clinical Research Associate during on-site monitoring visits. Should the storage temperature be outside the range, the medication must be quarantined immediately and the Sponsor contacted for guidance.

6.7.3 Accountability

The Investigator is responsible for the storage and accountability of the IMP supplies. The Investigator will ensure that adequate records of the receipt, dispensation and return of the IMP are kept and that the study drug is used only for subjects enrolled in the study. Subjects should be instructed to return all used and unused IMP dispensed to them at each scheduled visit. All data regarding the study drug (including medication (kit) and batch numbers) must be recorded in the eCRF and on any other relevant forms provided.

The study site will maintain a drug inventory/dispensing record for all IMP dispensed and returned. At the end of the study, a copy of the drug inventory/dispensing record should be sent to the Sponsor for the central study file. The original will be kept in the site files.

After completion of the study, or if it is prematurely terminated, all unused material will be returned to Vifor Pharma. All used IMP containers will be retained at the site by the Investigator/qualified designee for the Study Monitor's verification. The decision to destroy study medication at site must be made by Vifor Pharma. If the study medication is destroyed at site, the Investigator will forward the certificate of destruction to Vifor Pharma.

6.7.4 **Procedures for Overdose**

Based on the mode of action of VIT-2763, excessive doses of VIT-2763 could cause acute hypoferraemia. In addition it theoretically may warrant acute medical management following transient changes in serum iron parameters, in particular if concurrent (additional) blood loss or haemolysis is suspected or if Hb measurements are low enough to cause symptoms of decreased oxygen delivery. Whilst it is unlikely that this may occur under the controlled environment of this study and based on dose-response relationship examinations obtained from the first-in-human trial in healthy subjects, further dosing in any affected subjects must be stopped immediately, and depending on the observed or reported signs or symptoms of the subject, standard medical care should be provided.

- In case any subject warrants medical care during the course of the study, the Investigator will be permitted to prescribe treatment(s) at his/her discretion, in order to protect the subject's safety and well-being and according to acceptable standards of medical care.

Any concomitant treatment given for any reason during the course of the study must be recorded on the eCRF and in the subject's medical records, including dosage, start and stop dates and reason for use.

RISKS/PRECAUTIONS 7.

7.1 **Special Warnings and Precautions for Use**

The safety and tolerability and preliminary efficacy of multiple doses of VIT-2763 in adult and adolescent patients with NTDT and documented iron overload will be investigated in this Phase 2a clinical trial.

The results of a Phase 1 clinical trial in healthy subjects revealed that treatment with single oral doses of VIT-2763 ranging from 5 mg to 240 mg and 7-day treatment with VIT-2763 oral doses of 60 mg QD, 120 mg QD, 60 mg BID and 120 mg BID was well tolerated and no SAEs were reported and no discontinuations due to AEs were reported. There were also no findings of clinical relevance with respect to vital signs, 12-lead ECG, telemetry or physical examination. With limited clinical data about previously observed adverse reactions from human studies being available, no serious adverse drug reactions (ADRs) are considered expected by the Sponsor for the purpose of expedited safety reporting of SUSARs and annual/aggregate safety reporting though.

Based on the known pharmacology, nonclinical studies including repeated dose toxicity data, and the available clinical data in adult healthy volunteers to date with VIT-2763, no safety concern is expected for the intended use in a paediatric population of adolescents (12 years and above) for a 3-month treatment duration.

Excessive doses of VIT-2763 could cause acute hypoferraemia. Based on nonclinical data, ECG monitoring is recommended, and standard emergency treatment should be applied. Caution should be exercised in subjects with:

- Developing iron deficiency during treatment.
- A Grade 4 anaemia including Hb < 8.0 g/dl (5.0 mmol/l) for female subjects or < 8.5 g/dl (5.3 mmol/l) for male subjects, and with an absolute Hb drop from baseline >2 g/dl for males and females, according to FDA toxicity grading scale for healthy adult and adolescent volunteers [14].

Based on the nonclinical safety findings, caution should be exercised in subjects with:

- History or clinical finding of cardiac disorders such as clinically relevant cardiac arrhythmia, cardiomyopathy, coronary disease, valve disorder, or heart failure.
- Prior or concomitant use of any medication slowing cardiac conduction (PR and QRS interval prolongation), or that prolongs the QT/QTc interval.

Due to the lack or limited data of nonclinical studies of the effect of VIT-2763 on pregnancy, fertility, and lactation at this stage of development, women of childbearing potential and male subjects must use highly effective methods of contraception whilst taking VIT-2763 and for 1 month after the last dose of VIT-2763. Breastfeeding must be

discontinued during treatment with VIT-2763 and for 3 months after the last dose of VIT-2763.

7.1.1 Contraception and Lactation

Due to the lack of nonclinical studies of the effect of VIT-2763 on pregnancy, fertility and lactation at this stage of development, women of childbearing potential and male subjects must use highly effective methods of contraception, as defined below, whilst participating in this study and for 1 month after the last dose of study medication, and breastfeeding must be discontinued during the study as of the first dose of the study medication.

Highly effective methods of contraception for female subjects participating in this study are:

- Intra-uterine device
- Bilateral tubal occlusion
- Vasectomised partner
- Sexual abstinence
- Subject has been surgically sterilised at least 6 months prior to the study

For female subjects participating in this study, continuous use of hormonal contraception alone is not sufficient, because potential interactions via CYP enzymes may alter the efficacy of hormonal contraception. The continuous use of hormonal contraception by a female subject should be combined with the use of a condom by the male partner; the condom should then be used together with a spermicide or adequate and approved alternatives.

Highly effective methods of contraception for men participating in this study are:

- Partner using highly effective method of contraception for women as listed above
- Partner using continuous hormonal contraception
- Surgical sterilisation
- Sexual abstinence

Male subjects must practice true abstinence or agree to use a condom during sexual contact with a pregnant female or a female of childbearing potential while participating in the study, and for at least 1 month (sufficiently exceeding 5 times the mean $t_{1/2}$ of VIT-2763 based on multiple dose human PK data) following investigational product discontinuation, even if he has undergone a successful vasectomy.

8. STUDY PROCEDURES

8.1 Description of Study Assessments

The following description of the assessments performed in this trial refers to the study days when the assessments are carried out. Prior to SIV the monitor had collected as much information as possible regarding the current impact of COVID-19 pandemic on site's ability to conduct the clinical trial and about the capacity of the site to face the reoccurrence of COVID-19 restrictions when managing enrolled subjects. The information for their site is documented in the 'VIT2763_THAL-201: COVID-19 mitigation plan_site specific information' tracker. An overview of the assessments with the visit numbers are displayed in Table 1.

8.1.1 Demographics and Medical History

Subject's demographics (gender, age, race, and ethnicity) and baseline characteristics including body weight, body mass index, and a medical history will be taken during the baseline visit. Information to be collected will include the aetiology and clinical presentation of β -thalassaemia, and the date when β -thalassaemia was first diagnosed, and other clinically relevant past and present medical conditions which were diagnosed/occurred up to at least 12 months prior to signing the informed consent and/or for which the subject is currently treated. Any medically important conditions sustained by the subject which extend beyond 12 months prior to informed consent, should also be reported in the medical history eCRF. Also, the date of the last RBC transfusion obtained will be recorded in the eCRF.

8.1.2 Symptoms and Signs of Anaemia

The Investigator must assess signs and symptoms associated to anaemia in β -thalassaemia:

- Fatigue, weakness
- Shortness of breath
- Pale or yellowish skin
- Deformities of the facial bones
- Slow growth, growth retardation
- Abdominal swelling
- Dark urine

Any new clinically relevant symptom or sign of worsening of β -thalassaemia associated anaemia, or any other comorbidity, as assessed by the Investigator, must be reported as an AE (see Section 10).

The β-thalassaemia associated genotype, clinical presentation and RBC transfusion needs received during the past 24 weeks prior to randomisation which are part of the inclusion criteria, must be documented in the source data (see Section 5.2).

Physical Examination and Vital Signs 8.1.3

The body systems to be assessed in the physical examination include general appearance, head (eyes, ears, nose and throat), cardiovascular, respiratory, abdominal, musculoskeletal, neurological, lymph nodes, and skin. In the study, physical examination is performed at screening Visit V1 (i.e., Day -28 to -1) and on Visit V3 (Day 1), and V8 (Day 84). Facultative physical examinations can be performed on indication, i.e., symptom-directed, on all other visits.

Vital signs measurements include diastolic blood pressure, systolic blood pressure, and pulse rate. Vital signs are assessed at screening Visit V1 and on Visits V3 to V8. Vital signs should be performed at V3 to V8 before IMP dosing, after a resting period of at least 5 minutes. Any new clinically relevant change as assessed by the Investigator, in blood pressure readings, pulse rhythm or rate must be reported as an AE (see Section 10).

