40-59	60-placebo	60-placebo	60	1.0-1.5
	60-60	60-60	120	2.0-3.0
	Placebo- placebo	Placebo- placebo	N/A	N/A
60-100	120-placebo	120-placebo	120	1.2-2.0
	120-120	120-120	240	2.4-4.0
	Placebo- placebo	Placebo- placebo	N/A	N/A

¹ Estimated total daily dose/kg body weight range based on individual plasma pharmacokinetic parameters versus dose level/body weight obtained from human Phase 1 study. Notes: N/A=Not applicable; TDD=Total daily dose.

All treatments will be administered either at the study site in the context of study visits, or by the subjects at home from Day 1 to Day 84.

The study medication (VIT-2763 and/or matching placebo) will be administered for all subjects twice a day to maintain the blind, in the morning and in the evening.

Capsules (VIT-2763 and/or matching placebo) will be administered approximately 1 hour after meals at the same clock time (between 08:00 and 10:00 am for the morning dose, and between 20:00 and 22:00 pm for the evening dose, respectively). Food intake, except for water ad libitum, should be avoided for at least 1 hour prior to and 1 hour after the morning and evening dose administration.

Inclusion Criteria:

- 1. Documented diagnosis of NTDT, including a β -thalassaemia intermedia-phenotype.
- 2. NTDT is defined as subjects having received <5 units of red blood cells (RBCs) during the 24-week period prior to randomisation/first drug administration of VIT-2763 or placebo (Day 1; 1 unit is defined as 200 to 350 ml of transfused packed RBCs and last RBC transfusion must have been received ≥14 days prior to randomisation).

Note: Subjects who are supposed to receive RBC transfusions after randomisation in the Investigator's opinion, and according to local practise, and having received at least 1 dose of VIT-2763, may be considered to stay on study treatment for safety reasons, and in case there are no tolerability concerns. Subjects will be censored for secondary efficacy.

3. Male and female adult* NTDT subjects, 18-65 years of age inclusive (Cohort I only) at time of screening.

- * Following section in italics is applicable for dedicated Thailand site(s) as per local site Ethics Committee (EC)/Institutional Review Board (IRB) guidance:
- Male and female adult NTDT subjects, 20-65 years of age inclusive (Cohort I only) at time of screening.
- Male and female adolescent* NTDT subjects, 12-17 years of age inclusive (Cohort II only) at time of screening.

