Haemoglobin local ⁽⁹⁾		×	×	×	×	×	×	×	
VIT-2763 PK(10)			×			×	×	×	
Adverse events	×	X	×	×	×	×	×	×	×
Prior/concomitant medications	×	×	×	×	×	×	×	×	×
Study drug dispensation			×	×	×	×	×		
Study drug administration(12)			×	×	×	×	×	×	
Study drug accountability				X	X	X	X	X	

Any outstanding criteria not available on Day -15 (screening Visit 2) to be available before randomisation.

Body systems to be assessed include general appearance, head (eyes, ears, nose and throat), cardiovascular, respiratory, abdominal, musculoskeletal, neurological, lymph nodes and skin.

At 2-3 hours post-administration post-morning dose

Biochemistry sample including electrolyte status (sodium, potassium, magnesium, calcium, chloride), total bilirubin, urea, uric acid, creatinine, total protein, alkaline phosphatase, aspartate aminotransferase, alanine aminotransferase, gamma-glutamyl transpeptidase, glutamate dehydrogenase, lactate dehydrogenase, haptoglobin, amylase, bicarbonate, unconjugated bilirubin, creatine phosphokinase, folic acid, Vitamin B₁₂, albumin, glucose, total cholesterol, and triglycerides. Clotting: prothrombin time, activated partial thromboplastin time, For female subjects only; beta-human chorionic gonadotropin in serum at screening and V8 (Samples will be derived from serum biochemistry tube); in urine at baseline and all other visits. thrombin time. Serum ferritin, serum iron, unsaturated iron binding capacity, calculated transferrin saturation (screening visit only); all parameters will be assessed centrally

will be assessed centrally. Samples will be collected PD measurements include serum iron, serum ferritin, serum transferrin, unsaturated iron binding capacity, calculated transferrin saturation,

on Visits 3 to 8 approximately 2 hours post-dose

Haematology sample to assess Hb will be taken locally at study site and results must be available at day of dosing (sample at optional Visit V2) 9

PK samples will be collected on Visit 3 and Visit 7 at pre-dose trough and at approximately 1 hour and 4 hours post-dose, and on Visits 6 and 8 at pre-dose trough and approximately at 1 hour and 3 hours

Ξ

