1.2.3 Summary of Completed Clinical Studies

A Phase 1 study in healthy subjects with the title "A Phase 1, Double-blind, Randomised, Placebo-controlled Study on the Safety, Tolerability, Pharmacokinetics and Pharmacodynamics of Single and Multiple Ascending Doses of VIT-2763 in Healthy Subjects", Protocol No. VIT-2763-101, EudraCT No. 2017-003395-31, has been performed.

The study consisted of a single ascending dose part (Part A) and a multiple ascending dose part (Part B) to assess the safety, tolerability, PK and PD of ascending single and multiple oral doses of VIT-2763. The primary endpoint in this first-in-human study was to collect the incidence of AEs and SAEs by means of the changes in vital signs, clinical laboratory, 12-lead ECG and cardiac telemetry examinations and physical examination findings following single and multiple oral doses compared to baseline.

Secondary endpoints were to characterise the PK of VIT-2763 and to measure PD parameters to identify potential surrogate markers of VIT-2763 mechanism of action after single or multiple oral dosing.

Treatment with single oral doses ranging from 5 mg to 240 mg and 7-day treatment with oral doses of 60 mg QD, 120 mg QD, 60 mg q12h and 120 mg q12h were well tolerated by healthy male and female subjects. Following single dose all treatment-emergent adverse events (TEAEs) were of mild severity. There were no SAEs reported and no discontinuations due to AEs. Following 7-day repeated treatment all TEAEs were mild or moderate. There were no SAEs reported and no discontinuations due to AEs. There were no findings of clinical relevance with respect to vital signs, 12-lead ECG, telemetry or physical examination.

PK analyses revealed that the initial oral absorption of VIT-2763 was relatively fast, most subjects had detectable levels already at 15-30 minutes post-dose and T_{max} for VIT-2763 ranged from 0.50 hours to 3 hours post-dose. A second peak or shoulder in the concentration time profile was observed around 3-4 hours post-dose (from 15 mg dose).

The exposure over the dose range of 5 mg to 240 mg was slightly more than dose proportional for C_{max} , AUC_{0-last} and AUC_{0-inf} .

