Following multiple oral dose for 7 days up to 120 mg q12h there was no apparent change in absorption and accumulation was minimal. The apparent volume of distribution following single oral administration was moderate ranging from 64.3 to 145 l indicating moderate distribution to tissues. The geometric mean $t_{1/2}$ ranged from 1.9 to 5.3 hours following single oral dosing and from 2.07 to 3.80 hours on Day 1 and from 2.61 to 5.26 hours on Day 7 following repeated dosing.

Following both single and multiple dosing, a temporary decrease in mean serum iron levels and a temporary decrease in mean calculated % TSAT was seen at all VIT-2763 dose levels between 4 and 12 hours post-dose. Following both single and multiple dosing, a temporary increase in mean serum hepcidin levels was seen at doses of 60/120/240 mg for single dosing and at all VIT-2763 multiple dose levels. Maximum mean serum hepcidin levels were observed between 1 and 4 hours post-dose for the highest single dose levels of 60 mg, 120 mg and 240 mg, and for all 4 multiple dose levels. No dose-related effects were observed with respect to serum ferritin, serum transferrin, serum EPO and serum sTFR levels on both Day 1 and Day 7.

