3.4 Primary Endpoint(s)

3.4.1 Primary Safety Endpoints

- Reported or observed AEs: by SOC and PT (MedDRA coded term), by severity and relation to study product in each treatment group.
- Reported or observed SAEs: by SOC and PT (MedDRA coded term), by severity and relation to study product in each treatment group.
- Changes in vital signs (blood pressure and pulse rate), clinical laboratory safety tests (haematology, serum biochemistry, coagulation, and urinalysis), 12-lead ECG, and physical examination findings.

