6.4.2.1 VIT-2763

Total daily dose of 60 mg, 120 mg or 240 mg VIT-2763, to be taken orally from Day 1 to Day 84 as per randomisation scheme and schedule. Capsules are to be taken in the morning in conjunction with water approximately 1 hour after meals between 08:00 to 10:00 a.m. At study visits, subjects are asked to stay in the hospital until up to 4 hours at selected visits for PK sampling. At 2-3 hours post administration a 12-lead ECG will be conducted. To maintain the BID dosing schedule, i.e., after having received a dose in the morning at the hospital, the subjects will be advised to take the study medication in the evening approximately 1 hour after meals and with water at approximately the same clock time each day between 08:00 p.m. and 10:00 p.m. in the evening.

One dosage strength (60 mg) is available and will be used accordingly to achieve the specified doses.

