9.1.4 Post-randomisation Visits V4 (Week 1) to V8 (Week 12 or Early Discontinuation)

- Subjects will return to the out-patient clinic at 1 (±1 day), 2 (±2 days), 4 (±3 days), 8 (±3 days) and 12 weeks (±3 days) after randomisation.
- If a subject cannot return to the site for a study visit due to COVID-19 pandemic, the Investigator will conduct a remote visit (e.g., telemedicine, phone call), a visit at the subject's home, or in facilities near to the subject's home to evaluate subject safety and eligibility to continue the study therapy, if applicable and as per local country guidance.
- At the remote/home visits the Investigator should at minimum perform the following: evaluation of the subject's general condition, collection of information on any new and ongoing adverse events, collection of information on the IMP intake and concomitant medications use. Scheduled urine samples may be collected at a home visit, or in laboratories near to the subject's home and should be processed locally. Scheduled blood samples may also be collected at home visit or laboratories near to the subject's home and sent to the central laboratory if possible, otherwise processed locally. Safety analyses such as haematology panel (RBC, Hb, haematocrit, mean corpuscular volume, mean corpuscular Hb, mean corpuscular Hb concentration, white blood cell count with differential, platelets count), coagulation (prothrombin time, activated partial thromboplastin time, thrombin time) and liver function tests (ALT, AST, GGT, total bilirubin, alkaline phosphatase) should be done at the minimum.
- Subjects will have to come in the morning of the visit before taking the study medication, and have to come on an empty stomach. Drinking of water ad libitum is allowed. If a subject is not able to visit the site for IMP resupply due to COVID-19 pandemic, a direct shipment of the study drug to the patient home/place of stay can be implemented, if allowed by the local regulations. The shipment will be performed by a logistics provider in a traceable and temperature-controlled manner.

- During the out-patient visits, the Investigator will check the vital signs (including weight at V8 only), also for AEs, check concomitant medication. On Visit 8 also a physical examination will be done.

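### Scheduled on-treatment blood pressure is read only before dosing, so an acute asymptomatic effect near peak exposure cannot be seen

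*Protocol*

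**What the plan says.** Protocol section 3.4.1 includes in the primary safety endpoints "Changes in vital signs (blood pressure and pulse rate), clinical laboratory safety tests"; SAP section 2.6.1 does the same. Protocol section 8.1.3 sets the timing: "Vital signs should be performed at V3 to V8 before IMP dosing, after a resting period of at least 5 minutes". Section 9.1.4 ensures that the visit-day dose has not been taken on arrival: "Subjects will have to come in the morning of the visit before taking the study medication". Table 1 has no post-dose vital-sign timepoint. SAP section 5.7.4 summarises values and change from baseline by visit, with baseline as the last value before first dose, and defines no post-dose reading.

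The ECG is handled differently. Section 6.4.2.1 states: "At 2-3 hours post administration a 12-lead ECG will be conducted". The Table 1 footnote for V3 to V8 agrees: "At 2-3 hours post-administration post-morning dose". Section 8.1.4 has ventricular rate recorded on that ECG. SAP section 5.7.3 lists it for evaluation at baseline, 2 h post-dose on Day 1 and every treatment visit. The change-from-baseline summaries in protocol section 12.8.1 and SAP section 5.7.3 name PR, QRS, QT and QTcF only.

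**The concern.** VIT-2763 is absorbed quickly and has a short half-life. A reading taken just before the next dose is therefore taken when little drug is present, most of all in the QD arm, where the evening capsules are placebo (Table 2). The protocol places the ECG within the Tmax range but plans no blood pressure there.

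The planned table compares a drug-free baseline (V3 pre-dose) with trough values at V4 to V8. It can show a sustained or cumulative shift. It cannot show a transient fall or rise in the hours after a dose unless the subject has symptoms. The two active arms are also read at different relative exposures, which complicates the display by dose frequency. Neither document tells the reader of those tables that the values are trough values.

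**Working it through.** The plan states no figure for the interval from dose to reading or for residual exposure, so there is none to reproduce. Both are derived here.

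**Inputs**
- Dosing windows (Synopsis, administration schedule): "between 08:00 and 10:00 am for the morning dose, and between 20:00 and 22:00 pm for the evening dose".
- Evening capsules in the QD arm are placebo (Table 2).
- Tmax (section 1.2.3): "ranged from 0.50 hours to 3 hours post-dose".
- Half-life as a range of geometric means (section 1.2.3): "from 2.61 to 5.26 hours on Day 7 following repeated dosing".
- Accumulation over 7 days was minimal (section 1.2.3), so earlier doses are ignored.

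**Step 1: interval from last active dose to the next morning dose.** Vital signs come just before that dose.
- QD: nominally 24 h. From 10:00 to 08:00 the next day is 22 h; from 08:00 to 10:00 is 26 h.
- BID: nominally 12 h. From 22:00 to 08:00 is 10 h; from 20:00 to 10:00 is 14 h.

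**Step 2: residual share of peak.** With one-compartment decay starting at Tmax, share = 2^(-(t - Tmax)/t½). Example, QD with Tmax 3 h and t½ 5.26 h: (24 - 3)/5.26 = 3.99 half-lives, and 2^(-3.99) = 6.28%.

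| Arm and interval | t½ 2.61 h, Tmax 0.5 h | t½ 2.61 h, Tmax 3 h | t½ 5.26 h, Tmax 0.5 h | t½ 5.26 h, Tmax 3 h |
|---|---|---|---|---|
| QD, 24 h | 0.19% | 0.38% | 4.52% | 6.28% |
| BID, 12 h | 4.72% | 9.16% | 21.97% | 30.54% |

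Across the full clock windows the ranges are 0.1-8.2% for QD (22-26 h) and 2.8-39.8% for BID (10-14 h).

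**Step 3: sensitivity to the second peak.** Section 1.2.3 reports a second peak or shoulder at about 3-4 h. Counting decay from 4 h raises the upper ends to 2^(-20/5.26) = 7.2% (QD) and 2^(-8/5.26) = 34.8% (BID). The picture does not change.

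**Step 4: exposure at the ECG.** The 2-3 h ECG lies inside the Tmax range. Even if Tmax were 0.5 h, the share of peak at 3 h would be 2^(-2.5/2.61) = 51% to 2^(-2.5/5.26) = 72%.

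**Step 5: what is observed near peak.**

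| Measure | Pre-dose, V3-V8 | 2-3 h post-dose, V3-V8 | Change from baseline named for the post-dose value |
|---|---|---|---|
| Blood pressure | Yes | No | No reading to summarise |
| Heart rate | Yes (pulse) | Yes (ECG ventricular rate) | No |
| PR, QRS, QT, QTcF | No | Yes | Yes |

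**The case against.** Several arguments on the other side carry weight.

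- **Heart rate.** A reader might infer that pulse, like blood pressure, is invisible near peak. The documents do not support that: ventricular rate is recorded 2-3 h post-dose at V3 to V8 and evaluated under SAP section 5.7.3. What remains is that its change from baseline is not named.
- **Overdose text.** Section 6.7.4 mentions hypotensive subjects, and a reader might take this as a blood pressure signal. It concerns overdose, calls conduction effects very unlikely, and mentions hypotension only as a feature of cases that may need treatment. It does not predict a blood pressure effect at trial doses.
- **Phase 1.** Single doses up to 240 mg and 7 days up to 120 mg every 12 hours gave no clinically relevant vital-sign findings. This lowers the prior concern. It does not settle the point: those subjects were healthy, multiple dosing lasted 7 days, and the documents do not give the times of the vital-sign readings.
- **Trough readings have value.** They are standardised and taken at rest, and they can show sustained or cumulative effects over 12 weeks. Phase 1 serum iron and transferrin saturation fell between 4 and 12 h post-dose, so plasma peak is not the only time of interest. The BID trough is not drug-free. Clinically relevant changes noticed by the investigator must be reported as adverse events.
- **No claim is planned.** A reader might infer that a flat table would be presented as proof of haemodynamic safety. All analyses are descriptive, without tests or decision rules, and neither document plans that statement. The narrower point is that the tables are not labelled as trough.
- **Confounding of a post-dose change.** Time of day and meals differ between the two readings, so the change needs the placebo arm. At 20 adults allocated 8:8:4, that is 4 subjects. This limits precision but does not remove the value of having the reading.

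**Conclusion.** The point holds for blood pressure. Every scheduled on-treatment reading is a trough value: about 24 h after the last active dose in the QD arm (about 0.2-6% of peak) and about 12 h in the BID arm (about 5-31% of peak). An acute asymptomatic effect near peak would go unseen. Heart rate near peak is collected through the ECG but not carried into the change-from-baseline summaries.

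The percentages assume one-compartment decay from Tmax, nominal dosing intervals, and Phase 1 half-lives that are geometric means in healthy subjects. Individual patients may lie outside them. The intervals of 24 h and 12 h do not depend on that model.

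This is not a contradiction in the plan, and the documents give no sign that a blood pressure effect is expected at trial doses. It is a gap in observing a primary safety endpoint under exposure, and it is cheap to close.

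**What to change.** - **Protocol section 8.1.3 and Table 1:** keep the pre-dose set. Add one blood pressure and pulse reading at V3 to V8 just before the existing 2-3 h post-dose ECG, after the same 5-minute rest.
- **SAP section 5.7.4:** summarise the change to 2-3 h post-dose both from the same visit's pre-dose value and from the V3 pre-dose value, by visit and arm, read against placebo. Label the existing vital-sign tables as pre-dose/trough.
- **SAP section 5.7.3 (and protocol section 12.8.1):** add ventricular rate to the change-from-baseline summaries.

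The cost is a few minutes per visit, one eCRF field set, a Table 1 footnote and one table. Subjects are already on site after dosing at V3 to V8 for the ECG and the PD sample at about 2 h. If readings can no longer be added, the labelling and the ventricular-rate summary can still be done from data already planned.
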